12.7 Follow-up Procedures for Adverse Events

The investigator may be asked to provide follow-up information to the GW PVD for any AEs reported or during the investigation of potential safety issues. Such requests for additional safety information may occur post Visit 8, after the trial.

AEs considered related to the IMP by the investigator or the sponsor should be followed up until resolution or the event is considered stable.

It will be left to the investigator's clinical judgment if an AE is of sufficient severity to require the participant's removal from treatment. A participant may also voluntarily withdraw from treatment due to what he or she perceives as an intolerable AE. Further details of withdrawal are presented in Section 10. If either of these occurs, the participant must undergo an EOT assessment and be given appropriate care under medical supervision until symptoms cease or the condition becomes stable. If a safety concern is identified following withdrawal of a participant, GW may contact the investigator for additional follow-up information.

12.8 Potential Cases of Drug-induced Liver Injury

All investigational sites are required to submit to the GW PVD the laboratory results for any participant after randomization that meets the criteria for the selected laboratory parameters as follows:

Confidential Page 74 of 104

EudraCT Number: 2019-003369-16 Clinical Protocol Global V3, 23Mar2021

- Serum ALT or AST > 3 × ULN with the appearance of fatigue, nausea, vomiting, right upper quadrant pain or tenderness, fever, rash, and/or eosinophilia (> 5%).
- ALT or AST $> 8 \times ULN$.
- ALT or AST $> 5 \times$ ULN for more than 2 weeks.
- ALT or AST \geq 3 × ULN and (TBL \geq 2 × ULN or INR \geq 1.5).

These reports must be sent to the GW PVD via email (see Appendix 2) within 24 hours of becoming aware of the results. In addition, please send a copy of the participant's baseline laboratory results with all reports to the GW PVD.

Abnormal values in AST and/or ALT concurrent with abnormal elevations in TBL that meet the criteria outlined above are considered potential cases of drug-induced liver injury and will be considered as protocol-defined criteria for treatment discontinuation and important medical events. The investigator will arrange for the participant to return to the investigational site as soon as possible (within 24 to 48 hours of notice of abnormal results) for repeat assessment of ALT, AST, TBL, alkaline phosphatase, and GGT, detailed history and physical examination. Participants should be followed in this way until all abnormalities have normalized (in the investigator's opinion) or returned to the baseline state. However, if the above transaminase elevation criteria are confirmed by the first set of follow-up laboratory tests, the participant must be withdrawn from the trial.

Elevations in ALT or AST $> 3 \times \text{ULN}$ or TBL $> 2 \times \text{ULN}$ alone are not considered potential cases of drug-induced liver injury, but will be followed as detailed above, within 72 hours' notice of abnormal results. If the participant cannot return to the investigational site, repeat assessments may be done at a local laboratory and the results sent to GW PVD.

12.9 Notification of Safety Information to Investigators, Regulatory Authorities and Institutional Review Board or Independent Ethics Committee

In accordance with the EU Clinical Trials Directive, relevant parts of the FDA Code of Federal Regulations and any national regulations, GW will inform investigators, regulatory authorities and relevant IRBs/IECs of all relevant safety information. This will include the reporting of relevant SAEs and all suspected unexpected serious adverse reactions (SUSARs). This information will be provided through 2 sources:

Confidential Page 75 of 104

SPONSOR: GW RESEARCH LIMITED

Study Code: GWAP19030 EudraCT Number: 2019-003369-16 Clinical Protocol Global V3, 23Mar2021

1. Investigator's Brochure (IB)⁴²: a compilation of the clinical and non-clinical safety data available on the IMP that is relevant to the trial. The IB is updated annually or when important new safety information becomes available.

2. Council for International Organizations of Medical Sciences (CIOMS) reports: these reports are issued every time a SUSAR is reported to GW. They provide information on individual case reports and are sent to all the regulatory authorities, the relevant central ECs which have approved the trial and investigators. As required, the investigator should notify their regional IRBs/IECs of SAEs or SUSARs occurring at their site and other AE reports, i.e., CIOMS reports and any additional safety documentation received from GW, in accordance with local procedures.

In the US, investigators are normally required to report promptly to their IRBs all unanticipated problems involving risks to participants, or others, including AEs that should be considered unanticipated problems. Based on current FDA guidance the following clarification is provided in determining what constitutes an unanticipated problem:

In general, an AE observed during the conduct of a trial should be considered an unanticipated problem involving risk to participants and reported to the IRB, *only* if it were unexpected, serious, and would have implications for the conduct of the trial (e.g., requiring a significant, and usually safety-related, change in the protocol such as revising inclusion/exclusion criteria or including a new monitoring requirement, informed consent, or IB). An individual AE occurrence *ordinarily* does not meet these criteria because, as an isolated event, its implications for the trial cannot be understood.

The FDA guidance states that, accordingly, to satisfy the investigator's obligation to notify the IRB of unanticipated problems, any investigators participating in a multisite trial may rely on the sponsor's assessment and provide to the IRB a report of the unanticipated problem prepared by the sponsor.

GW will inform investigators, regulatory authorities and relevant IRBs/IECs of any safety issues or case reports that are considered to be unanticipated and provide such reports as mentioned above. It should be noted that a single SUSAR report notified to investigators in the trial does not necessarily constitute an unanticipated problem unless identified by GW in the submission cover letter.

As a minimum, the recipient will be sent all of the above and relevant updates between the period from ethical approval and final database lock.

EudraCT Number: 2019-003369-16 Clinical Protocol Global V3, 23Mar2021

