10 INVESTIGATIONAL MEDICINAL PRODUCT DISCONTINUATION AND WITHDRAWAL

In accordance with the Declaration of Helsinki, the International Council for Harmonisation (ICH) Harmonised Guideline: Integrated Addendum to ICH E6(R1): Guideline for Good Clinical Practice (GCP) E6(R2), the FDA regulations relating to GCP and clinical trials, the EU Clinical Trials Directive, the EU GCP Directive and/or other applicable regulations, a participant has the right to withdraw from the trial at any time and for any reason, with no obligation to provide a reason, and without prejudice to his or her future medical care by the physician or at the institution.

The participant must be permanently discontinued from IMP if any of the following apply:

- Administrative decision by the investigator, GW, or a regulatory authority.
- Withdrawal of participant consent.
- Lost to follow-up.
- Pregnancy.
- QTcF \geq 500 msec (average of 3 measurements).
- Suicidal ideation or behavior of type 4 or 5 during the treatment period, as evaluated with the adult C-SSRS or based on investigator assessment.
- Protocol deviation that is considered to potentially compromise the safety of the participant or validity of data collected.
- ALT or AST > 3 × ULN with the appearance of fatigue, nausea, vomiting, right upper quadrant pain or tenderness, fever, rash, and/or eosinophilia (> 5%).
- ALT or AST $> 8 \times ULN$.
- ALT or AST $> 5 \times$ ULN for more than 2 weeks.
- ALT or AST $> 3 \times$ ULN and (TBL $> 2 \times$ ULN or INR > 1.5).

Note: Prior to treatment discontinuation for the transaminase elevations noted above, the investigator may choose to confirm the transaminase elevations by repeating the following laboratory tests within 24 to 48 hours: ALT, AST, TBL, INR, % eosinophils, gamma-glutamyl transferase (GGT), and alkaline phosphatase. Should the above transaminase elevation criteria be confirmed, the participant must permanently discontinue IMP. In cases where

Study Code: GWAP19030

EudraCT Number: 2019-003369-16 Clinical Protocol Global V3, 23Mar2021

transaminase elevation IMP discontinuation criteria are not met or confirmed, the dose of a concomitant medication with known hepatotoxicity may be reduced.

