Abbreviations: BACS = Brief Assessment of Cognition for Schizophrenia; BAS-MPsQ = Basic Personal Traits Module of Multidimensional Psychological Questionnaire; CDSS = Calgary Depression Scale for Schizophrenia; CGI-S = Clinical Global Impression-Severity; CGI-I = Clinical Global Impression-Improvement; C-SSRS = Columbia-Suicide Severity Rating Scale; ECG = 12-lead electrocardiogram; EOT = end of treatment; ESRS= Extrapyramidal Symptom Rating Scale; ET = early termination; EXP-MPsQ = Expectation Module of Multidimensional Psychological Questionnaire; MINI = Mini-International Neuropsychiatric Interview; PER-MPsQ = Perception Module of Multidimensional Psychological Questionnaire; PGIC = Patient Global Impression of Change; PK = pharmacokinetics; PANSS = Positive and Negative Symptoms Scale; SQLS = Schizophrenia Quality of Life Scale; WOCBP = Women of childbearing potential.

- a. If a participant discontinues IMP prematurely (i.e., after Visit 3 but before the end of the treatment period) they are required to complete an EOT visit and complete the safety follow-up visit 2 weeks after their last dose. Participants who discontinue IMP prematurely should be encouraged to attend any outstanding trial visits. An ET visit should only be completed if the participant prematurely discontinues IMP and withdraws from the trial without continuing trial visits as per the trial schema.
- b. Video to be watched prior to administration of PANSS.
- c. Age of first use, duration since first regular use (years), current use within the last month, regular use once per week or more, and most common route of current administration (smoked, vaped, oral) will be recorded at screening. Number of days used in last 7 days and average grams used per day will be collected weekly via ePRO from Visit 2 using the IMP adherence monitoring Platform.
- d. A full physical examination at screening and a symptom-directed physical examination at Visit 3 and Visit 7.
- e. Height will be collected at screening only.
- f. To be collected prior to clinical laboratory assessments and PK sampling.

EudraCT Number: 2019-003369-16 Clinical Protocol Global V3, 23Mar2021

- g. Vital signs will include systolic/diastolic blood pressure, heart rate, respiratory rate, and temperature. Blood pressure should be taken after the participant has been in a supine position in a rested and calm state for at least 5 minutes. Blood pressure must be recorded using the same arm throughout the trial, where possible.

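### The Section 12.8 repeat panel for isolated ALT/AST above 3 × ULN omits INR and % eosinophils, either of which could complete a Section 10 stopping criterion while IMP continues

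*Protocol*

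**What the plan says.** Protocol Section 12.8 lists the liver findings that sites must report. It then describes follow-up for "Abnormal values in AST and/or ALT concurrent with abnormal elevations in TBL that meet the criteria outlined above": a return within 24 to 48 hours "for repeat assessment of ALT, AST, TBL, alkaline phosphatase, and GGT", with a detailed history and physical examination, continued until the abnormalities have normalized or returned to baseline. ALT or AST above 3 × ULN, or TBL above 2 × ULN, "alone are not considered potential cases of drug-induced liver injury, but will be followed as detailed above", within 72 hours. If the participant cannot return, a local laboratory may do the repeat.

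Protocol Section 10 sets the rules for permanent discontinuation of IMP. One is ALT or AST above 3 × ULN "with the appearance of fatigue, nausea, vomiting, right upper quadrant pain or tenderness, fever, rash, and/or eosinophilia (> 5" percent). Another is ALT or AST above 3 × ULN together with TBL above 2 × "ULN or INR > 1.5". The other two are ALT or AST above 8 × ULN, and above 5 × ULN for more than 2 weeks. A note says that, before stopping for such an elevation, the investigator "may choose to confirm the transaminase elevations by repeating the following laboratory tests within 24 to 48 hours: ALT, AST, TBL, INR, % eosinophils", GGT and alkaline phosphatase. Where "transaminase elevation IMP discontinuation criteria are not met or confirmed, the dose of a concomitant medication with known hepatotoxicity may be reduced"; nothing in that case requires IMP to stop.

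Scheduled chemistry and hematology are drawn at Visits 1, 3, 5 and 7 (Protocol Appendix 1; SAP Section 5.7.3.1). Table 9.1.11-1 places INR in the biochemistry panel and the white-cell differential in hematology.

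**The concern.** An isolated transaminase elevation above 3 × ULN is not itself a reason to stop, so the participant can go on taking IMP while being followed. Whether IMP must later be stopped depends on what the follow-up finds. Two of the findings that would turn permission to continue into an obligation to stop are laboratory values that the follow-up does not ask for. A site that does exactly what Section 12.8 lists would be compliant and could still miss a mandatory stop. At stake is continued exposure in a participant for whom the protocol itself says exposure must end.

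**Working it through.** No sample size, power or alpha figure is involved. The check compares two lists and then uses the visit schedule to bound the gap.

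**Panels.** The Section 10 note names 7 tests: ALT, AST, TBL, INR, % eosinophils, GGT and alkaline phosphatase. Section 12.8 names 5: ALT, AST, TBL, alkaline phosphatase and GGT. The difference, 7 − 5 = 2, is INR and % eosinophils.

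**Routes to a stop.** Start from ALT or AST above 3 × ULN alone, with IMP continuing, and split the Section 10 transaminase criteria into the findings that could complete them:

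| Finding that completes a Section 10 stop | What would show it | Required by Section 12.8 follow-up? |
|---|---|---|
| A listed symptom or sign, including rash | History and examination | Yes |
| Eosinophilia above 5% | White-cell differential | No |
| ALT/AST above 8 × ULN | ALT, AST | Yes |
| ALT/AST above 5 × ULN for more than 2 weeks | Repeated ALT, AST | Yes |
| TBL above 2 × ULN | TBL | Yes |
| INR above 1.5 | INR | No |

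Four of the six routes are covered and two are not. For TBL above 2 × ULN alone the panel is adequate, because the repeated ALT and AST would show completion of the combined criterion.

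**Does the Section 10 panel fill the gap?** No. It is optional, and it is written for elevations that already meet a discontinuation criterion. An isolated elevation above 3 × ULN falls outside it.

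**How long the gap can last.** An elevation found at a scheduled visit has an INR and a differential from the same visit, so the first classification is sound. What can be missed is a later change. The on-treatment laboratory visits after Day 1 are Day 29 and Day 85, each with a window of ±3 days:

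- Nominal: 85 − 29 = 56 days.
- Shortest with windows: (85 − 3) − (29 + 3) = 82 − 32 = 50 days.
- Longest with windows: (85 + 3) − (29 − 3) = 88 − 26 = 62 days.

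This supposes that no unscheduled INR or differential is taken. It is an upper bound, because both missing criteria also need ALT or AST above 3 × ULN. Those two enzymes are repeated. Once they are at or below 3 × ULN, neither INR nor eosinophils can complete a stop; if they pass 8 × ULN, or stay above 5 × ULN for more than 2 weeks, IMP stops anyway.

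**How many.** The documents give no rate of isolated elevations. As an illustration only, assume 1% to 10% of active participants. If the 80 randomized (SAP Section 3.2) were split 2:1, about 80 × 2/3 = 53 received active drug, which gives 0.5 to 5 with such an elevation at any time. That is a loose ceiling under the assumed rates: it includes elevations first found at Day 85, and only some of the rest would go on to cross the INR or eosinophil threshold.

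**The case against.** The strongest reply is that the cover is already substantial. Each of the four Section 10 transaminase criteria has at least one limb that Section 12.8 follow-up can detect, so no criterion is wholly unmonitored. The index sample at a scheduled visit includes both missing tests. Section 9.1.11 requires clinically significant results to be followed up as clinically appropriate, investigators may add tests, and they may stop IMP on judgment. Elevations first seen at Day 85 come when treatment is ending, and Section 9.1.11 separately requires clinically significant abnormal end-of-treatment results to be repeated. All of this stands, and it sets the limits of the point. It does not remove it: a mandatory stopping rule is left to depend on tests that nothing requires in this subgroup.

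A reader might go further in three ways that the documents do not support.

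- *That established liver cases stay on drug or go unmonitored.* For AST/ALT elevation with raised TBL, the panel measures what is needed. A case that already qualifies through INR or eosinophils alone must stop IMP under Section 10. Appendix 1 says of participants who stop early that "they are required to complete an EOT visit and complete the safety follow-up visit 2 weeks after their last dose", and that EOT visit includes chemistry and hematology. For these cases the Section 12.8 panel only fails to confirm the qualifying limb or to show that it has normalized.
- *That 56 days is the expected delay.* It would require ALT or AST to stay above 3 × ULN until Day 85 with no other stop and no extra sample.
- *That an assumed rate applied to the 244 planned active participants (2 × 122) counts those exposed to the gap.* That would include Day 85 elevations, and recruitment ended at 80 randomized in all.

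**Conclusion.** The point holds in a narrow form. Section 12.8 sends isolated ALT/AST above 3 × ULN, in participants who may remain on IMP, to a panel without INR or % eosinophils, although either can complete a Section 10 stop. The exposure is confined to INR-only or eosinophilia-only crossings, with no listed symptom and no TBL above 2 × ULN, that arise after the index sample while ALT or AST remains above 3 × ULN and IMP continues. After a Day 29 signal it lasts at most 56 days (50 to 62 with windows) and usually should end sooner. This rests on the index sample being a scheduled one and on no unscheduled INR or differential being drawn. The number affected is unknown and probably small. It is a cheap improvement in patient safety with no bearing on the efficacy analysis.

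**What to change.** In Section 12.8, add INR and % eosinophils to the repeat panel whenever ALT or AST is above 3 × ULN, so that it matches the Section 10 note. Isolated TBL above 2 × ULN needs no change. No further wording is needed to bring in isolated transaminase elevations, because Section 12.8 already sends them to the same follow-up.

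The cost is one line of protocol text and two routine assays, both already listed in Table 9.1.11-1. They would be taken at a blood draw that is already required, with no added visit. Up to two extra tubes may be needed, since that table lists prothrombin time as plasma and the differential under whole blood. As the trial terminated early, the practical benefit lies in any remaining follow-up and in later protocols that reuse this text.

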4 EXPERIMENTAL PLAN

4.1 Trial Design

This is a randomized, double-blind, placebo-controlled, parallel-group, outpatient trial. The trial will compare the efficacy and safety of 2 dose levels of GWP42003-P (150 mg twice daily [b.i.d.] and 500 mg b.i.d.) versus placebo in participants with schizophrenia who are experiencing an inadequate response to ongoing antipsychotic treatment.

The duration of the trial will be approximately 20 weeks, which includes a screening period (up to 4 weeks), a single-blind placebo run-in period (2 weeks), a double-blind treatment period (12 weeks), and a safety follow-up period (2 weeks).

After signing the informed consent form (ICF), participants will enter the screening period (Visit 1). The investigator will submit participants' eligibility forms for clinical surveillance and training (CST) review. The CST will evaluate the eligibility of participants and provide the outcome of the evaluation to the site. Participants cannot be enrolled until site personnel have received the final CST notification. Additional details for CST will be described in the study manual. At Visit 2 screened participants who continue to meet eligibility criteria will be randomized 1:1 to receive 150 mg b.i.d. or 500 mg b.i.d. dose matched volumes of placebo in a single-blind manner for the placebo run-in period. At Visit 3 (Day 1), participants who continue to meet the required eligibility criteria will be randomized 2:1 to receive GWP42003-P or placebo of equivalent volume to their placebo run-in allocation (Table 7.1-1) in a double-blind manner for the treatment period.

Randomization will be stratified by region (North America, Europe) and by sex (male, female).

A safety follow-up visit will be conducted 2 weeks after the last dose of IMP. If a participant discontinues IMP prematurely (i.e., before the end of the treatment period) they are required to attend an end of treatment (EOT) visit (±3 days) and complete the safety follow-up visit 2 weeks after their last dose. Participants are encouraged to attend any outstanding visits per the trial schema. If a participant prematurely discontinues IMP and withdraws from the trial without continuing trial visits as per the trial schema, they are required to attend an early termination (ET) visit upon withdrawal and complete the safety follow-up visit 2 weeks after their last dose.

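### Protocol Section 12.8 takes a participant with a confirmed liver event out of the trial, where Section 10 only stops IMP; following 12.8 can lose later PANSS scores

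*Protocol*

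**What the plan says.** Protocol Section 12.8 lists four liver criteria and then says that "if the above transaminase elevation criteria are confirmed by the first set of follow-up laboratory tests, the participant must be withdrawn from the trial". Earlier in the same paragraph it says that transaminase abnormalities with concurrent bilirubin elevation meeting the criteria "will be considered as protocol-defined criteria for treatment discontinuation and important medical events". The next paragraph adds that ALT/AST or bilirubin elevations "alone are not considered potential cases of drug-induced liver injury".

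Protocol Section 10, and the synopsis in the same terms, gives essentially the same four criteria as reasons to stop IMP: "Should the above transaminase elevation criteria be confirmed, the participant must permanently discontinue IMP". It does not ask for the participant to leave the trial. Section 12.7, on adverse events that lead to removal from treatment, points to Section 10 and says: "If either of these occurs, the participant must undergo an EOT assessment".

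The protocol treats stopping IMP and leaving the trial as different states. For those who stop IMP early, Section 4.1 says: "Participants are encouraged to attend any outstanding visits per the trial schema"; footnote a of Appendix 1 repeats this: "Participants who discontinue IMP prematurely should be encouraged to attend any outstanding trial visits". For those who also leave the trial, Section 4.1 says "they are required to attend an early termination (ET) visit upon withdrawal", and footnote a reserves the ET visit for them.

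The analysis follows the same split. SAP 5.1.1.1 uses scores collected after IMP is stopped if the participant stays in the study. Under Protocol 13.6.1 and SAP 5.5.2.1, a participant who withdraws has one last assessment, which is assigned to the nearest scheduled visit.

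**The concern.** Two mandatory instructions for the same confirmed safety event lead to different data collection. Under Section 10 the participant stops IMP and is asked to keep attending. Under Section 12.8 PANSS collection ends at the ET visit. Nothing visible in either document says which section prevails, and about 55 sites were expected.

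At stake is the score at Day 85, the primary time point, after an event that may be drug-related. The plan intends to keep scores after IMP discontinuation, and Section 12.8 as written works against that intention.

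**Working it through.** There is no planned figure to reproduce. The check is a comparison of the texts, followed by the timing and size of the loss.

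**1. Same event?** Both sections list ALT or AST above 3 × ULN with symptoms or eosinophilia, above 8 × ULN, above 5 × ULN for more than two weeks, and 3 × ULN with raised bilirubin or INR. The fourth is printed with ≥ in Section 12.8 and > in Section 10. That may come from text conversion, and nothing here depends on it. The criteria referred to in the Section 12.8 withdrawal sentence could be all four or only the cases with concurrent bilirubin elevation that open the paragraph. On either reading the two sections conflict, at least for the concurrent-bilirubin cases.

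**2. Different consequence?** Withdrawal also stops IMP, so both routes satisfy Section 10 on dosing. They differ in what follows:
- *Section 10 route:* EOT visit, remaining visits encouraged, and any later scores analysed at their own visits.
- *Section 12.8 route:* earlier scores stay in the MMRM, one ET score is added at the nearest visit, and nothing is collected afterwards.

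**3. Is Day 85 lost when the event is found at Week 4?** Inputs from the documents:
- Scheduled post-baseline chemistry is at Day 29 and Day 85 only (Appendix 1; SAP 5.7.3.1).
- The visit window is ±3 days.
- The repeat draw is 1 to 2 days after notice (Section 12.8).

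Assumptions: 1 to 8 days for each laboratory result, and the ET visit on the day of confirmation.

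- Midpoints between visits: (29 + 57)/2 = 43 and (57 + 85)/2 = 71.
- Week 4 sample: Day 26 to 32.
- Earliest ET visit: 26 + 1 + 1 + 1 = Day 29. Latest: 32 + 8 + 2 + 8 = Day 50.
- If the ET visit may slip by 3 days: 50 + 3 = Day 53.

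The ET score maps to Day 29 or Day 57, depending on turnaround, so it can still supply a Week 8 value. It does not reach Day 85. For that, a Day 32 sample would need a lag of at least 40 days (32 + 40 = 72 > 71), or 37 days with a 3-day slip (32 + 37 + 3 = 72). The result is therefore not sensitive to the assumed turnaround.

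This range does not cover the criterion of more than 5 × ULN for over two weeks, because no upper limit is set on when the second qualifying sample is drawn. That is why the loss is described as general, not certain. An event found at the Week 12 chemistry costs no score, since PANSS is scheduled at that visit.

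**4. Size per event.** At most one Day 85 score. With 80 randomized and one third expected in each active arm, 80/3 = 26.7 and 1/26.7 = 3.75%. As planned, 1/122 = 0.82%.

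**5. Power, as background.** The documents give no event rate; assume 1% to 10% in the 500 mg arm. Power = Φ(4.32/SE − 1.96), with SE = 11 × √(1/n₁ + 1/n₂).
- With 309/3 = 103 per arm: SE = 1.533, power 80.5%.
- At 1%, the active arm has 103 − 0.85 × 1.22 = 101.96: power 80.3%.
- At 10%, it has 103 − 0.85 × 12.2 = 92.6: SE = 1.575, power 78.3%.

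These figures take every affected completer as lost and allow no top-up of recruitment.

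**The case against.** The strongest reply is that Section 12.8 contains a slip of wording. The protocol uses withdrawal loosely elsewhere: footnote h of Appendix 1 calls the 500 msec QTcF limit a withdrawal criterion, although Section 10 lists it only as a reason to stop IMP. The same Section 12.8 paragraph speaks of stopping treatment. Sites may well have followed Section 10. This stands in part: divergent practice is possible, not shown. But Section 12.8 names the trial explicitly, and footnote a gives leaving the trial a specific operational meaning.

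It also stands that visits after stopping IMP are only encouraged, so Section 10 does not secure a Day 85 score. Nothing is lost for a participant who would not have attended Week 12 anyway. The trial has ended early with 80 randomized, so an edit recovers none of their scores.

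Three stronger readings are tempting and are not supported:
- *A bias of known size or direction in the treatment comparison.* No liver-event rate is given, and any text under Protocol 13.6.1.1 (sensitivity analysis) and 13.6.6 (missing data) is not visible.
- *A loss of power.* Protocol 13.1 allows 15% drop-out and a top-up to 309 evaluable participants, and SAP 5.5.1 now plans no formal test.
- *Exact cut-off days for losing the Day 85 score with every criterion and every unscheduled sample.* Laboratory turnaround is not in the documents, and the ±3-day window may apply to the ET visit. For the two-week criterion, a second sample on Day 55 with an 18-day lag (8 + 2 + 8) gives Day 73, which maps to Day 85.

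**Conclusion.** The conflict is real and sits in the current protocol text. Section 12.8 requires withdrawal from the trial where Section 10, for essentially the same confirmed criteria, requires only that IMP be stopped. Following Section 12.8 can cost PANSS scores that the plan would otherwise seek and analyse, generally including Day 85 for an event found at the Week 4 chemistry.

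The effect is small and its total cannot be quantified. The Week 4 timing rests on the assumed turnaround but would change only with a lag of several weeks. The point is worth correcting because a mandatory instruction ends efficacy collection after a possibly drug-related event, against the plan's own intent. It does not undermine the analysis.

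**What to change.** In Protocol Section 12.8, replace the withdrawal instruction with wording such as: *the participant must permanently stop IMP (see Section 10) and be encouraged to attend every remaining trial visit*. State in the same place whether this applies to all four listed criteria or only to cases with concurrent bilirubin elevation.

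For the 80 already randomized, identify any withdrawals made under Section 12.8, with the visit at which they occurred, within the withdrawal reasons that SAP 5.4.1 already summarizes. The planned liver-parameter listing can support this. Readers can then see which missing Week 12 scores, if any, came from this instruction.

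The cost is one protocol sentence and its clarification of scope. No new table, visit or procedure is needed.
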